1 LIST OF ABBREVIATIONS

Abbreviation	Definition
ACEI	Angiotensin-Converting Enzyme Inhibitor
AE	Adverse Event
ARB	Angiotensin Receptor Blocker
AUC	Area Under the Curve
CC	Coordinating Center
Cr	Creatinine
CRF	Case Report Form
DCRI	Duke Clinical Research Institute
DSMB	Data Safety Monitoring Board
ECG	Electrocardiogram
EDC	Electronic Data Capture
EF	Ejection Fraction
eGFR	Estimated Glomerular Filtration Rate
ER	Emergency Room
GDMT	Guideline Directed Medical Therapy
GFR	Glomerular Filtration Rate
HF	Heart Failure
HFN	Heart Failure Clinical Research Network
HFpEF	Heart Failure with Preserved Ejection Fraction
HFrEF	Heart Failure with Reduced Ejection Fraction
ITT	Intention To Treat
IRB	Institutional Review Board
IV	Intravenous
KCCQ	Kansas City Cardiomyopathy Questionnaire
LV	Left Ventricular
LVAD	Left Ventricular Assist Device
LVEDP	Left Ventricular End Diastolic Pressure
LVEF	Left Ventricular Ejection Fraction
m	Meters
mmHG	Millimeters of mercury
mmol/L	Millimole per liter
MDRD	Modification of Diet in Renal Disease
NHLBI	National Heart, Lung, and Blood Institute
NT-proBNP	Pro-B-type Natriuretic Peptide
NYHA	New York Heart Association
PCI	Percutaneous Coronary Intervention
PCW	Pulmonary Capillary Wedge
PO	“Per os,” or by mouth
PPI	Patient Package Insert
SAE	Serious Adverse Event
SBP	Systolic Blood Pressure
VO ₂	Oxygen Consumption

3 EXECUTIVE SUMMARY

Title	Entresto™ (LCZ696) In Advanced Heart Failure (LIFE Study)
Indication	New York Heart Association (NYHA) Class IV heart failure with a reduced ejection fraction (EF ≤ 35%).
Location	Approximately 40 clinical centers in the United States
Brief Rationale	
Patients with advanced heart failure with reduced ejection fraction (HFrEF) have extremely high morbidity and mortality with 1 year outcomes of death and hospitalization of approximately 50%.^{1,2} For the most advanced heart failure patients, the evidence base for medical treatment is limited with consensus guidelines recommending consideration for either cardiac transplant or ventricular assist device, or palliative care.³
 
The PARADIGM-HF trial showed that LCZ696, which consists of the neprilysin inhibitor sacubitril and the ARB valsartan, improved morbidity and mortality in patients with chronic HFrEF in comparison to enalapril.¹ However, limited experience with advanced heart failure patients was gained from patients enrolled in the trial. Additionally, experience is needed on the use of, and outcomes with, LCZ696 in patients unable to tolerate target doses of ACEI/ARB compared to reduced doses of LCZ696.
 
Hypothesis: In patients with symptomatic heart failure due to left ventricular systolic dysfunction, treatment with LCZ696 for 24 weeks will improve NT-proBNP levels, which reflect hemodynamic and clinical status, compared to treatment with valsartan.

Study Design	This study will be a randomized, double-blinded trial of advanced heart failure subjects with 1:1 randomization to either LCZ696 (sacubitril and valsartan) or valsartan. Study drug will be administered in a double-dummy fashion, in which subjects take active (LCZ696 or valsartan) and placebo. Approximately 400 subjects will be randomized into the study.
Treatment	LCZ696 (sacubitril and valsartan) plus placebo or valsartan plus placebo
Primary Objective and Endpoint	The proportional change from baseline in the AUC for NT-proBNP levels measured at 2, 4, 8, 12 and 24 weeks
Secondary Objectives and Endpoints	
 1. Days alive and out of hospital at 24 weeks, not listed for transplant (Status 1A, 1B or 1-4) or undergoing transplant, implanted with an LVAD, maintained or started on continuous inotropic therapy for ≥ 7 days, or has had two hospital admissions for HF (other than the index admission*) 
*The days alive and out of hospital will end on the day of the second readmission.
 
 2. Tolerability measured as:

	
a) Number of subjects achieving a target dose of 25%, 50% or 100% of valsartan or LCZ696b) Number of subjects developing hypotension (SBP \leq 85 mmHg) with symptomsc) Number of subjects developing worsening renal function (eGFR $<$20 ml/min/1.73m²)d) Number of subjects developing moderate (\geq 5.5 mmol/L) or severe (\geq 6 mmol/L) hyperkalemia
--	--

4 OBJECTIVES

4.1 Primary Objectives

To evaluate the effects of LCZ696 compared to valsartan on the proportional change from baseline in the AUC for NT-proBNP levels at 2, 4, 8, 12, and 24 weeks.

Hypothesis: In patients with symptomatic, advanced heart failure due to left ventricular systolic dysfunction, treatment with LCZ696 for 24 weeks will improve NT-proBNP levels, which reflect hemodynamic and clinical status, compared to treatment with valsartan.

4.2 Secondary Objectives

1. To evaluate the effects of LCZ696 compared to valsartan over 24 weeks on days alive and out of hospital at 24 weeks, not listed for transplant (Status 1A, 1B or 1-4) or undergoing transplant, implanted with an LVAD maintained or started on continuous inotropic therapy for ≥ 7 days, or has had two hospital admissions for HF (other than the index admission*)
*The days alive and out of hospital will end on the day of the second readmission.
2. To determine tolerability measured as:
 - a. Number of subjects achieving a target dose of 25%, 50% or 100% of valsartan or LCZ696
 - b. Number of subjects developing hypotension (SBP ≤ 85 mmHg) with symptoms
 - c. Number of subjects developing worsening renal function (eGFR < 20 ml/min/1.73 m²)
 - d. Number of subjects developing moderate (≥ 5.5 mmol/L) or severe (≥ 6 mmol/L) hyperkalemia

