7.3 Study Intervention Phase

Study treatment will be titrated to the target dose of 200 mg LCZ696 (equivalent to Entresto™ 97/103 mg) as two 100 mg LCZ696 and 2 placebo tablets po BID or valsartan 160 mg (two 80 mg valsartan and 2 placebo tablets) po BID.* Randomized subjects will receive the first dose of study drug as follows:

[figure not shown]
- For subjects not previously taking ACEI or ARB, previously taking ACEI or ARB at a low dose*, or subjects who have an eGFR < 30 mL/min/1.73m², the starting dose of valsartan will be 40 mg po BID and the starting dose of LCZ696 will be 50 mg po BID.
- For subjects taking an ARB at greater than low dose†, the starting dose of valsartan will be 80 mg po BID and the starting dose of LCZ696 will be 100 mg po BID.
- For subjects taking an ACEI at greater than low dose†, the ACEI will be withheld for ≥ 36 hours prior to randomization. The starting dose of valsartan will be 80 mg po BID and the starting dose of LCZ696 will be 100 mg po BID.

* Per package insert, the valsartan compounded in Entresto™ is more bioavailable than the valsartan in other marketed formulations. The dose equivalence for valsartan compounded in Entresto™ compared to valsartan prepared alone (Entresto™ dose = marketed valsartan dose) is as follows: 26 mg=40 mg, 51 mg=80 mg, 103 mg=160 mg.

† Low dose is defined as 24 hour dose of ≤ 10 mg lisinopril, ≤ 5 mg ramipril, ≤ 50 mg losartan, ≤ 10 mg olmesartan, or other dose equivalent.

Dose adjustments will be performed every 2 weeks by doubling the dose of LCZ696 or valsartan up to the target maximum dose. The doses of LCZ696 are 50 mg (one 50 mg active and 1 placebo tablet), 100 mg (one 100 mg active and 1 placebo tablet) and 200 mg (two 100 mg active and 2 placebo tablets). These doses are equivalent to 24/26 mg, 49/51 mg, and 97/103 mg commercial Entresto™, respectively. The doses of valsartan are 40mg (one 40 mg active and 1 placebo tablet), 80 mg (one 80 mg active and 1 placebo tablet), and 160 mg (two 80 mg active and 2 placebo tablets). The criteria for doubling the dose will be based on systolic blood pressure (a SBP > 90 mmHg is required for up titration), changes in renal function (maximum serum creatinine of 2.0 mg/dL), and the absence of symptoms of hypotension. For those not tolerating the current dose of study drug, the dose will be down-titrated to the previous tolerated dose. Subjects will return to clinic for follow-up visits at 2, 4, 8, 12, 24 and 26 weeks after randomization.

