8 STUDY FLOW DIAGRAM

The Screening visit and Visit 1 may be combined at the investigator's discretion for subjects who are stable, and for whom lab results have been reviewed as long as the investigator ensures the 1st dose of LCZ696 is \geq 36 hours after last ACEI dose (if applicable). If not combined, Visit 1 should take place within 7 days of the Screening Visit

Visit 4: 4 weeks post-randomization

Second dose titration:

If tolerating current dose (SBP > 90 mmHg, Cr ≤ 2.0 mg/dL, and no symptoms of hypotension) then double dose.

- Maximum dose LCZ696 200 mg po BID or valsartan 160 mg po BID (2 active and 2 placebo tablets po BID)

If not tolerating dose, reduce to previously tolerated dose

Assessments: interim history, review of medications, physical examination, KCCQ, routine laboratory testing, core laboratory testing (BNP, NT-proBNP and Cystatin C), and AE monitoring

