10.4 Dosing Guidelines

The study will begin with a 3-7 day run-in period in which all subjects will be administered LCZ696 50 mg po BID. For those subjects taking ACEI prior to the run-in period, the first dose of LCZ696 will be withheld ≥ 36 hours after last ACEI dose. After stopping LCZ696, a 36 hour washout period is required before resuming an ACEI.

Subjects tolerating the LCZ696 in the run-in period will be randomized to either LCZ696 or valsartan. Doses will be assigned in the following fashion:

If previously taking no ACEI/ARB, low-dose ACEI/ARB[†], or eGFR < 30 ml/min/1.73m², ensure ACEI has been discontinued and the last dose was ≥ 36 hours ago, then

- LCZ696 50 mg plus placebo po BID or valsartan 40 mg plus placebo po BID

If previously taking greater than low dose ARB[†]

- LCZ696 100 mg plus placebo po BID or valsartan 80 mg plus placebo po BID*

If previously taking greater than low dose ACEI[†], ensure ACEI was discontinued and the last dose was \geq 36 hours ago, then

- LCZ696 100 mg plus placebo po BID or valsartan 80 mg plus placebo po BID*

* At Investigator discretion, study drug may be started at the low dose (LCZ696/placebo 50 mg po BID or valsartan/placebo 40 mg po BID) if there are any concerns regarding tolerability at the 100 mg / 80 mg dose.

Two weeks after randomization, upward dose titration will occur among subjects tolerating their current dose (SBP > 90 mmHg, creatinine (Cr) \leq 2.0 mg/dL, and no symptoms of hypotension). This will consist of doubling the dose up to a maximum dose LCZ696 200 mg po BID (two 100 mg tablets plus 2 placebo tablets po BID) or valsartan 160 mg po BID (two 80 mg tablets and 2 placebo tablets po BID). For those not tolerating the current dose of study drug, the dose will be down-titrated to the previous tolerated dose.

Two weeks after the prior dose titration visit and four weeks after randomization, further dose titration will occur among subjects tolerating their current dose (SBP > 90 mmHg, Cr \leq 2.0 mg/dL, and no symptoms of hypotension). This will consist of doubling the dose up to a maximum dose LCZ696 200 mg po BID or valsartan 160 mg po BID. For those not tolerating the current dose of study drug, the dose will be down-titrated to the previous tolerated dose. The total duration of study drug treatment will be 24 weeks.

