15.9 Anticipated Disease Related Events and Events of Interest

The following are anticipated, disease-related events in patients with HF or anticipated events of interest in patients with heart failure taking valsartan or valsartan/sacubitril:

- **Arrhythmias:** This refers to both atrial and ventricular arrhythmias.
- **Sudden Cardiac Death:** This refers to witnessed cardiac arrests and sudden deaths without an otherwise apparent cause such as trauma or malignancy.
- **Acute coronary syndrome:** This refers to unstable angina, non ST segment elevation myocardial infarction (NSTEMI), and ST segment elevation myocardial (STEMI).
- **Unplanned hospitalization, ER visit or clinic visit for worsening HF:** This refers to treatment for acute heart failure such as receiving intravenous diuretics.
- **Cerebrovascular event:** This refers to cerebrovascular accidents (stroke) of any cause (hemorrhagic, ischemic, or embolic) and transient ischemic attack (TIA).
- **Venous thromboembolism:** This includes both deep venous thrombosis and pulmonary embolus.
- **Lightheadedness, Presyncope, or Syncope:** This includes dizziness, lightheadedness, or fainting from any cause.
- **Worsening renal function:** This refers to acute kidney injury, typically defined as a decrease in eGFR \geq 20% over 48 hours, or progressive loss of renal function over time.
- **LVAD implantation:** This refers to implantation of a temporary or durable LVAD.
- **Cardiac Transplantation**
- **Hyperkalemia \geq 5.5 mEq/L**
- **Acute renal failure with serum creatinine $>$ 2.5 mg/dL**
- **Angioedema**
- **Symptomatic hypotension**

Anticipated events will not be captured as AEs/SAEs during the study, but will be entered on the appropriate electronic case report form (eCRF) module (“Events of Interest” page).

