## 10.2 – Secondary Endpoint #2

Endpoint Description: Tolerability measured as number of subjects achieving a target dose of 25%, 50% or 100% of valsartan or LCZ696, using the pre-COVID-19 population.

Response Variable Definition: Due to limited documentation concerning reasons for dose reduction, four versions of this endpoint will be calculated:

- 1) maximum study drug dose started (including 0),
- 2) dose patient took for the most number of days (including 0),
- 3) last dose patient was taking (including 0), and
- 4) last dose patient was taking (excluding 0).

There are 4 ordered values possible based upon the coding of the responses. Each response will be coded to represent 0% of target (no drug), 25% of target (50 mg LCZ696/40 mg Valsartan), 50% of target (100 mg LCZ696/80 mg Valsartan) or 100% of target (200 mg LCZ696/160 mg Valsartan). The number of evaluable days will be based on time from randomization to earliest date of Week 24, Death, Consent Withdrawal, or Last Contact.

Additional Covariates in Addition to Randomized Treatment: atrial fibrillation status at time of randomization

Handling of Dropouts and Missing Data: No adjustment will be made for missing data.

Sensitivity Analysis: Re-calculate the endpoint analysis using the original ITT population.

Statistical Tests: An ordinal logistic regression model (PROC LOGISTIC in SAS) will be used to estimate and statistically compare whether there is differential study drug dose achievement between the treatments.

Interpretation of Treatment Comparison: More patients achieving/tolerating higher doses indicates better tolerance of LCZ696 versus Valsartan.

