### 10.3 – Secondary Endpoint #3

Endpoint Description: Tolerability measured as number of subjects developing hypotension (SBP  $\leq$  85 mmHg) with symptoms, using the pre-COVID-19 population.

Response Variable Definition: Number of subjects with a documented event of interest of symptomatic hypotension defined as systolic blood pressure  $\leq$  85 mmHg between Randomization and the Week 24 assessment.

Additional Covariates in Addition to Randomized Treatment: atrial fibrillation status at time of randomization

Handling of Dropouts and Missing Data: Each patient will be evaluated based on the available follow-up. No adjustment for incomplete follow-up will be made.

Sensitivity Analysis: Re-calculate the endpoint analysis using the original ITT population.

Statistical Tests: A logistic regression model (PROC LOGISTIC in SAS) will be used to estimate and statistically compare whether there is differential rate of subjects developing symptomatic hypotension between the treatments.

Interpretation of Results: A lower rate of symptomatic hypotension defined as systolic blood pressure  $\leq$  85 mmHg indicates better tolerance of LCZ696 arm versus Valsartan.

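### Symptomatic hypotension at SBP above 85 mmHg, even if serious, enters no planned between-arm event comparison

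*Protocol*

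**What the plan says.** **Endpoint.** Protocol 4.2 sets as a tolerability measure the "Number of subjects developing hypotension (SBP ≤ 85 mmHg) with symptoms". The Executive Summary, Protocol 13.2 and SAP section 6 carry the same limit. SAP 10.3 defines the response as the "Number of subjects with a documented event of interest of symptomatic hypotension defined as systolic blood pressure" at or below 85 mmHg, from randomisation to the Week 24 assessment. It uses logistic regression adjusted for atrial fibrillation and reads a lower rate as better tolerance of LCZ696.

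**Titration.** Protocol 7.3 lists among the conditions for doubling the dose that "a SBP > 90 mmHg is required for up titration" "and the absence of symptoms of hypotension". The Visit 4 box in Protocol 8 puts these into a definition of tolerating: "If tolerating current dose (SBP > 90 mmHg, Cr ≤ 2.0 mg/dL, and no symptoms of hypotension) then double dose". Protocol 10.4 and 12.2 use the same definition, and 10.4 adds: "For those not tolerating the current dose of study drug, the dose will be down-titrated to the previous tolerated dose". The symptom condition carries no pressure limit.

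**Recording.** Protocol 15.9 names symptomatic hypotension among the events of interest without an SBP cut-off, and states: "Anticipated events will not be captured as AEs/SAEs during the study". These events go to the Events of Interest page. Protocol 15.10 repeats the exemption for SAEs and does not collect non-serious AEs on the safety page.

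**Comparisons.** SAP 13.1, the only safety analysis, compares SAEs by MedDRA preferred term. SAP 10.2 compares dose achieved and says of it: "Due to limited documentation concerning reasons for dose reduction, four versions of this endpoint will be calculated".

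**The concern.** The trial uses a wider notion of hypotension when it manages the dose than when it reports tolerability. A difference between a titration criterion and an endpoint threshold is not an error in itself. The difficulty is that the wider event, although named as an event of interest, falls between the two planned event analyses: the cut removes it from SAP 10.3 and the capture exemption removes it from SAP 13.1.

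Protocol 11.6 says that risks and benefits in advanced heart failure with lower enrolment blood pressure are unknown, and gives this as the rationale for the trial. It also singles out symptomatic hypotension, citing 18% against 12% in an earlier comparison with enalapril and stating no SBP threshold. A report that follows the SAP could conclude that LCZ696 was as well or better tolerated with respect to hypotension, and say nothing about symptomatic episodes above 85 mmHg.

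**Working it through.** **1. Follow one episode through the plan.** No arithmetic is needed. Take hypotensive symptoms at SBP 88 mmHg after randomisation.

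| Place | Rule | Does the episode count? |
|---|---|---|
| Protocol 8, 10.4, 12.2 (Weeks 2 and 4) | Tolerating requires SBP above 90 and no symptoms of hypotension | Not tolerating |
| Protocol 15.9 | Symptomatic hypotension, no SBP limit | Listed as event of interest |
| SAP 10.3 | Event of interest with SBP at or below 85 | No |
| SAP 13.1 | SAEs only; anticipated events are exempt | No, even if serious |
| SAP 10.2 (endpoint #2) | Dose achieved: 0, 25, 50 or 100% of target | Only if the dose changed or was held; cause not attributed |
| SAP 10.1 (endpoint #1) | Days in hospital, any unplanned admission | Only if admitted; cause not attributed |

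Symptoms at a pressure above 90 follow the same path, because the symptom condition has no pressure limit. Lightheadedness, presyncope and syncope are on the same exempt list in Protocol 15.9, so they offer no second route into the SAE table. No SAP section compares events of interest as a class. SAP 10.3 to 10.5 take only those that meet their own cuts.

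**2. Does the cut lower power?** The documents give no event rate or power for this endpoint, so there is no plan figure to reproduce. The following is scale only.

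Inputs: 335 patients in the pre-COVID-19 population (SAP section 3), assumed evenly split, so n = 335/2 = 167.5 per arm; two-sided alpha 0.05; 18% against 12% for all symptomatic hypotension (Protocol 11.6, another trial and comparator, so an assumption); and an assumed share of episodes that reach SBP 85 or less.

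Formula: power = Φ[(|p1 − p2| − 1.96·s0)/s1], with s0 = √(2·p̄(1 − p̄)/n), s1 = √((p1(1 − p1) + p2(1 − p2))/n) and p̄ = (p1 + p2)/2.

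For 18% against 12%: p̄ = 0.15, s0 = 0.0390, s1 = 0.0389, and (0.06 − 0.0765)/0.0389 = −0.42, so power is 34%.

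| Share reaching 85 or less (LCZ696 / comparator) | Rates | Expected patients | Power |
|---|---|---|---|
| All episodes | 18% / 12% | 30 / 20 | 34% |
| 75% / 75% | 13.5% / 9% | 23 / 15 | 26% |
| 50% / 50% | 9% / 6% | 15 / 10 | 18% |
| 25% / 25% | 4.5% / 3% | 7.5 / 5 | 11% |
| 50% / one third | 9% / 4% | 15 / 7 | 46% |

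With equal shares in both arms the narrow endpoint has less power than the wide one. If the excess lies in the deeper episodes, it has more. The shares are not in the documents, so the direction of the effect on power is open. It is low in every row.

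**The case against.** **The endpoint is a legitimate choice.** It is prespecified with the same limit in both documents, has an objective threshold, and need not match a cautious titration criterion. This stands, and is why the endpoint should stay.

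**Dose-limiting hypotension is not ignored.** A reader might infer that it enters no planned comparison at all. The documents do not support that. Endpoint #2 compares dose achieved in four versions, endpoint #1 counts days of any unplanned admission, and a death would enter tertiary endpoint #1. What is missing is a comparison of the event as an event. The SAP's own remark on poorly documented reasons for dose reduction means that endpoint #2 cannot reliably supply the cause.

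**The dosing rule can be over-read.** A reader might infer that SBP of 90 or less without symptoms always leads to dose reduction. Protocol 7.3 states the pressure condition for up-titration, so that is only one reading. The explicit criteria apply at Weeks 2 and 4; at Weeks 8 and 12 dose changes are discretionary. The point rests on the symptom condition alone. Nor do the documents say that dose reductions keep pressure above 85.

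**The eCRF is not available.** The wording of SAP 10.3 could mean that the Events of Interest page applied the cut of 85 itself, whereas Protocol 15.9 shows no cut. It therefore cannot be claimed that the recorded data would contradict a tolerance statement, and the fix must allow for either case.

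**Other provisions exist.** Protocol 16.3 sends monthly summaries of clinical and adverse events to the DSMB Chair, and 16.1 allows exploratory analyses. Neither is a prespecified between-arm comparison in the final report. It is also fair that the better-tolerance sentence in SAP 10.3 is direction wording repeated across endpoints and not a decision rule. That lowers the stakes but leaves the gap open.

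**Conclusion.** The gap is real and limited in extent. Symptomatic hypotension at SBP above 85 mmHg, including serious episodes, is compared between arms nowhere as an event. It can appear only as unattributed dose level or hospital days. This follows from the text of Protocol 15.9 and SAP 10.3 and 13.1, and needs no numerical assumption.

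The number of patients involved is unknown. A reader might infer from the equal-share rows that the cut weakens detection of an excess, but the last row shows the opposite under another equally unverified assumption. The case for a change is completeness of the safety comparison on a risk that the protocol itself highlights, and not power. This is a cheap improvement; it does not call the prespecified endpoint into question.

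**What to change.** In SAP 10.3:

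- Keep the SBP of 85 or less endpoint unchanged.
- Add a supportive by-arm comparison of patients with any symptomatic-hypotension event of interest from randomisation to Week 24, regardless of SBP. Use the same logistic model and atrial fibrillation covariate, in the pre-COVID-19 population and again in the original ITT population.
- Report the two results side by side, and limit any tolerance statement that rests on the narrow endpoint alone to symptomatic hypotension with SBP of 85 mmHg or less.
- State whether the Events of Interest page accepted episodes above 85. If it did not, the added comparison is not possible, and this should be stated as a limit on the conclusion.

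The cost is SAP wording and one extra model on data that should already be held, if the page recorded events as Protocol 15.9 describes. The downside is one more tolerability comparison, on a less specific event. The dosing rule is not touched.
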